4.2.2 Exclusion Criteria

Individuals not eligible to be enrolled into this protocol are those who:

- 1. Are pregnant or nursing, or of child bearing potential and not practicing an effective means of birth control;
- 2. Have a history of or current primary psychotic disorder or bipolar affective disorder type 1 or borderline personality disorder;
- 3. Are diagnosed with dissociative identity disorder or an eating disorder with active purging;
- 4. Have evidence or history of significant (controlled or uncontrolled) hematological, endocrine, cerebrovascular, cardiovascular, coronary, pulmonary, renal, gastrointestinal, immunocompromising, or neurological disease, including seizure disorder, or any other medical disorder judged by the investigator to significantly increase the risk of MDMA administration (Subjects with hypothyroidism who are on adequate and stable thyroid replacement will not be excluded);

- 5. Have hypertension using the standard criteria of the American Heart Association (values of 140/90 or higher assessed on three separate occasions [74]);
- 6. Have liver disease;
- 7. Have history of Diabetes Type I or II;
- 8. Have history of hyponatremia or hyperthermia;
- 9. Weigh less than 48 kg;
- 10. Would present a serious suicide risk or who are likely to require hospitalization during the course of the study;
- 11. Have used "Ecstasy" (material represented as containing MDMA) more than five times or at least once within 6 months of the MDMA session;
- 12. Require ongoing concomitant therapy with a psychiatric drug, including SSRIs, SNRIs, or MAOIs;
- 13. Meet DSM-IV criteria for substance abuse or dependence for any substance save caffeine or nicotine in the past 60 days;
- 14. Have glaucoma, significant atherosclerosis or hyperthyroidism;
- 15. Have any current problem, which in the opinion of the investigator or medical monitor, might interfere with participation in the study;
- 16. Are not able to give adequate informed consent.

5.0 Methods

5.1 Measures

The following outcome and safety measures will be used in Stage 1 and Stage 2:

5.1.1 Outcome Measures

The primary outcome measure will be the CAPS, a clinician-scored measure for PTSD diagnosis and measure of symptom intensity and severity. A qualified, blinded independent rater will perform the CAPS. The independent rater will not be present during the subject's experimental sessions nor have any information regarding the experimental sessions. Subjects will be instructed not to tell the independent rater any beliefs they or others have concerning their condition assignment during the evaluation session. The CAPS provides a standardized method to evaluate the frequency and intensity dimensions of each symptom, impact of symptoms on the subject's social and occupational functioning, overall severity of the symptom complex and global improvement since baseline and the validity of the ratings obtained. The CAPS interview takes approximately one hour to complete. The CAPS has been determined to have good internal consistency, concurrent validity, and test/retest reliability [75, 76]. An independent rater will assess all subjects at baseline and the end of Stage 1. The independent rater will also assess applicable subjects at the end of Stage 2 and 12 months after the subject's final experimental session.

The secondary measure of PTSD symptoms will be the PDS, a self-report measure designed to follow DSM IV criteria for assessing PTSD. The measure is derived from the Posttraumatic Symptom Scale – Self Report (PSS-SR), a measure also intended to tap into diagnostic criteria for PTSD. The PDS contains 49 items, with responses made on a

four-point scale, ranging from 0 ("not at all") to 3 ("five or more times a week"). The PDS consists of a list of 12 potential traumatic events, 12 items addressing elements of the traumatic event, of 17 symptom items, and nine items assessing impact on areas of life function [77]. Items addressing elements of the traumatic event and life function are answered as either present or not present (Yes or No). The seventeen items are summed to create a symptom severity scale. Cronbach's alpha for the symptom severity scale is 0.92. The PDS has test-retest reliability of 0.74 after a two-week and one-month interval, and subscales are inter-correlated, with correlations ranging from 0.73 to 0.82, and PDS scores had a moderate to good correlation with SCID diagnosis, with kappa = 0.65 [77]. The Hebrew translation of the 17-item symptom scale of the PDS will be used for this study [78, 79]. A study of the reliability and validity of the Hebrew translation has been conducted [80], with at least one report giving internal consistency of 0.94 [81].

The Beck Depression Inventory-II (BDI-II) is a 1996 revision of the BDI, a 21-item self-report measure [82, 83], that will serve as a measure of depression according to DSM-IV criteria[84]. The BDI-II has been validated, has high internal consistency and good test/re-test reliability and is not overly sensitive to daily variations in mood. It takes five to ten minutes to complete [84]. Score cutoffs indicate: 0-13 minimal depression, 14-19 mild depression, 20-28 moderate depression, and 29-63 severe depression. Higher scores indicate more severe depressive symptoms. The BDI-II has been translated and validated in Hebrew [85]. Subjects will complete the BDI-II at the same times as the CAPS.

The Global Assessment of Function (GAF) is a measure of quality of life and general function made through observations. The GAF consists of a single score, with scores ranging from 0 to 100, with 100 reflecting superior function and zero reflecting serious risk of causing harm to the self or others. The GAF is a reliable, validated measure of social functioning [86]. Subjects will complete the GAF at the same time as the CAPS.

The Pittsburgh Sleep Quality Index (PSQI) is a measure of self-reported sleep quality over a one month period. The PSQI was designed to be a reliable, standardized measure able to distinguish between good and poor sleepers. It consists of 19 items, with possible responses ranging from zero to 4 on a five-point scale [87]. The PSQI consists of seven sub-scales; sleep quality, sleep latency, sleep duration, habitual sleep efficiency, sleep disturbance, use of sleeping medications, and daytime dysfunction. These are all summed to produce a single global scale. Global scores can range from 0 to 21, with higher scores reflecting poorer sleep quality, and a score below 5 indicative of good sleep. It takes five to ten minutes to complete. Test-retest reliability ranges from 0.85 to 0.87, and it is internally consistent, with a Cronbach's alpha of 0.83[87, 88]. Global scores correlate with other measures of alertness and self-reported sleep quality [89]. The Hebrew translation will be used [90]. Analysis of the Hebrew translation found that it has a Cronbach's alpha of 0.70 in sleep clinic patients and 0.52 for non-clinic patients, with the lower alpha possibly the result of sleep clinic patients referred for snoring rather than insomnia.

The Reactions to Research Participation Questionnaire (RRPQ) [91] is an assessment of causes for taking part in research and responses to the experience of being a research

subject. Subjects will complete this measure during their final study visit, with exact time of completion varying in accordance with subject enrollment in the open label study segment or in the third open label MDMA-assisted psychotherapy session in Stage 2. The RRPQ is intended to assess the subject's experience as a research subject, perceived reasons for consenting to be a research subject and perceived freedom to take part in the study, and is not an outcome measure.

The long-term follow up questionnaire has been developed internally by the Sponsor to assess long-term benefits and harms of MDMA-assisted psychotherapy at the 12 month follow up visit. It will be translated into Hebrew.

All psychotherapy sessions, including experimental sessions, will be recorded to audio and video, with all recordings preserved for research purposes. Safety measures will be applied as described below to minimize risks associated with drug-assisted psychotherapy sessions.

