2.4 Rationale of Dose Selection

This study will compare the effects of psychotherapy sessions assisted by full or active placebo dose MDMA. Active placebo will be 25 mg MDMA followed one and a half to two and a half hours later by 12.5 mg, and the fully active dose will be 125 mg followed one and a half to two and a half hours by 62.5 mg.

Table 1. Dose Regimen

	Initial Dose	Supplemental Dose	Cumulative Dose
Active Placebo Dose	25 mg	12.5 mg	37.5 mg
Full Dose	125 mg	62.5 mg	187.5 mg

The full MDMA dose to be used in this study is identical to those used in previous studies in the U.S., Switzerland and Israel. Previous researchers have also used doses within this range [44, 45, 49, 56, 67, 68] [49, 67, 69-72]. Prior to the scheduling of MDMA, similar doses and regimens were used in psychotherapy [34, 36, 39]. The initial full dose is expected to produce all the commonly reported effects of MDMA. The supplemental dose will prolong subjective drug effects without producing physiological effects any greater than peak effects occurring after the initial dose.

The active placebo dose of MDMA was chosen on the basis of its demonstrated ability to produce detectable subjective effects in the absence of full therapeutic effects, thus serving as an active placebo [45, 70, 73]. These doses are expected to produce increases in positive mood and tension, but without the range of effects seen at higher doses. This dose was also used in the previous Swiss and Israeli studies conducted by the Sponsor.

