Results of HIV serology will be kept confidential, and appropriate referral for counseling will be made if necessary. The clinical laboratory values will be used to establish eligibility and will be kept with the subject's source record. The clinical laboratory values will not be captured in the CRF, but will be used to establish eligibility and will be kept with the subject's source record. Clinically significant abnormal vales will be captured as medical history. If, upon examination, there are questions raised about possible medical problems, the therapists will request a review of subject medical records and request additional tests or assessments as indicated.

An independent rater who will not be present during any of the therapy sessions will administer:

- SCID to assess eligibility
- CAPS to assess PTSD symptoms
- PDS to assess self-reported PTSD symptoms
- BDI-II to assess depression symptoms
- GAF to assess general psychological function
- PSOI to assess sleep quality

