5.2.7 Evaluation at End of Stage 1 and Unblinding (Visit 12)

The final evaluation in Stage 1 will occur two months after the second experimental session. This visit will consist of two meetings that may be completed on separate days, one with the independent rater and the other with the therapists.

- a. Subjects will meet the independent rater for at least an hour and a half.
- b. The blinded independent rater will administer:
 - CAPS to assess PTSD symptoms
 - PDS to assess self-reported PTSD symptoms
 - BDI-II to assess depression symptoms
 - GAF to assess general psychological function
 - PSQI to assess sleep quality
- c. The blinded independent rater will provide their belief of the subject's condition.
- d. After completing all assessments and measures with the independent rater, the subject will meet with the therapists for approximately 30 minutes.
- e. The therapists will assess suicidality with the C-SSRS.
- f. General wellbeing will be assessed.
- g. The blind will be broken for the subject's condition assignment. The independent rater will remain blind to condition assignment at this time.
- h. If the subject has received active placebo dose MDMA in Stage 1, the therapists will discuss enrollment in Stage 2. (See section 5.2.8)
- i. If the subject has received full dose MDMA in Stage 1 or the open label lead-in, or they elect not to participate in Stage 2, they will complete the Responses to Research Participation Questionnaire (RRPQ) and continue on to the 12-month Follow Up visit and study termination.
- j. Subjects who are not enrolled in Stage 2 may return to taking psychiatric medications if necessary.
- k. Subjects not enrolled in Stage 2 will receive a memory aid card for use between

this visit and the 12-month follow up. Subjects will use this card to record AEs, medications, and changes in psychiatric status that they will be asked about at the termination visit. Memory Aids will not be collected.

1. AEs and medications will be collected as described in Sections 8.5 and 9.0 of the protocol.

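### The requirement that the CAPS rater know nothing of the drug sessions is not carried into the instruction given to subjects or into the Visit 12 procedure

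*Protocol*

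**What the plan says.** Protocol 5.1.1 sets the intended condition: "The independent rater will not be present during the subject's experimental sessions nor have any information regarding the experimental sessions." The next sentence is the only rule on this matter addressed to subjects: "Subjects will be instructed not to tell the independent rater any beliefs they or others have concerning their condition assignment during the evaluation session."

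Other sections add protections. At screening, 5.2.1 describes the rater as someone outside all therapy: "An independent rater who will not be present during any of the therapy sessions will administer" the scales. At Visit 12, section 5.2.7 puts the ratings ahead of the therapist meeting at which the blind is broken: "After completing all assessments and measures with the independent rater, the subject will meet with the therapists for approximately 30 minutes." It then adds: "The independent rater will remain blind to condition assignment at this time." Section 5.4 says the same of the rater, and 5.3 has blinded staff carry out the evaluations of the randomised part. Section 5.2.7(c) also collects a guess: "The blinded independent rater will provide their belief of the subject's condition."

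SAP 9.9.1 makes the change in rater-scored CAPS-4 from baseline to Visit 12 the primary evaluation. SAP 9.9.3.1 tabulates correct guesses for subjects and therapists. The rater's guess is not in that analysis, although the SAP's own Table 2 (footnote I) schedules it at Visit 12.

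**The concern.** The condition in 5.1.1 concerns session information. The instruction meant to support it concerns opinions about allocation. A subject who says that his jaw was tight for hours, or that little happened in either session, has voiced no belief about assignment and has followed the instruction, yet has given the rater session information.

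This matters because CAPS at Visit 12 is a clinician's score, and rater blinding is its main defence against expectation bias. SAP 3.0 and 7.0 say the trial exists to supply effect-size estimates for later power calculations and a meta-analysis. Rater bias would enter that estimate directly, whether or not any test is performed.

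**Working it through.** **1. What each provision stops.**

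| Provision | What it stops or records | Does it stop a subject's account in the rating interview? |
|---|---|---|
| 5.1.1, no session information | States the intended condition | An account would breach it, but no step tells anyone how to prevent that |
| 5.1.1, instruction to subjects | Statements of belief about assignment, the subject's own or others' | No |
| 5.2.1, rater outside therapy | Direct observation | No |
| 5.2.2(k), information sheet | As described, covers conduct around dosing | No |
| 5.2.7, order of Visit 12 | Rating after assignment is known | No |
| 5.2.7(g) and 5.4, rater stays blind | Formal disclosure of assignment | No |
| 5.3, blinded evaluators | Staff knowledge of assignment | No |
| 5.2.7(c), rater's guess | Records a possible loss of blinding afterwards | No |

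**2. Could an account suggest the dose?** Protocol 2.4 says the low dose gives detectable subjective effects, but "without the range of effects seen at higher doses". Section 7.2 reports that in the earlier US study tight jaw, nausea, impaired gait or balance and sensitivity to cold were more frequent on MDMA than on placebo. It also reports five other reactions in 40% to 80% of participants in both conditions. That comparator was inactive (12.1), so its separation from MDMA need not carry over to 25 mg. An account may be informative, but the documents do not show that it identifies the arm.

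**3. Is there an occasion for it?** The rater meeting lasts at least an hour and a half (5.2.7(a)), and the CAPS covers global improvement since baseline (5.1.1). Nothing asks for session content, so disclosure would be incidental.

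**4. The plan's own figure, for scale only.** Protocol 12.1 states power 0.15 at effect size 0.8. For a two-sided 0.05 t-test with 3 and 5 subjects, df = 6 and the noncentrality is 0.8 / √(1/3 + 1/5) = 0.8 / 0.730 = 1.095. Power is then 0.153, so the figure reproduces. The present point does not depend on it.

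**5. Leverage of one rating.** A shift of s points in one score moves the full-dose mean by s/5 or the active placebo mean by s/3.

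**6. Illustration on assumed values.** None of these inputs is in the documents. Suppose a share q of interviews in each arm discloses the dose, and the rater then moves each such score by s points in the expected direction, down on full dose and up on active placebo. The bias in the arm difference is q·s + q·s = 2qs.

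- q = 0.25, s = 5: 2 × 0.25 × 5 = 2.5 points
- q = 0.5, s = 10: 2 × 0.5 × 10 = 10 points
- With an assumed SD of 20: 0.125 to 0.5 SD

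If instead there were no true effect and the arms differed only by a rater shift of 0.25, 0.5, 0.8 or 1.0 SD, the protocol's t-test would reject in 6.0%, 9.0%, 15.3% or 21.2% of trials. The SAP (9.0) amends that analysis and treats testing as exploratory (7.0), so the effect on the estimate matters more.

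**7. Would dropping flagged subjects help?** With three active placebo subjects, the chance that at most one remains is 3q²(1 − q) + q³. At q = 0.25 this is 0.141 + 0.016 = 0.156, about 16%. At q = 0.5 it is 0.375 + 0.125 = 0.50.

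**The case against.** A reader might infer that the belief instruction is the rater's only protection, and that subjects are free to recount their sessions. The documents do not support that. The preceding sentence in 5.1.1 requires the rater to have no session information, so an account would breach the protocol's stated intent. Absence from therapy, rating before unblinding and the recorded guess are also real protections.

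Other parts of the defence stand:

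- Therapists' opinions on assignment are already barred, because the instruction covers beliefs held by others.
- The supplemental dose is optional in both arms (2.4, 5.2.3(u), 6.2.1), so having taken it does not in itself reveal the arm.
- Visit 12 falls two months after the second session, and 5.2.7(b) gives the rater only the scales to administer.
- This is a pilot whose SAP calls any significance testing exploratory.

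These points limit the likelihood and weight of the problem. They do not remove it: a subject can comply fully with the instruction as written and still defeat the condition stated one sentence before it. The guess in 5.2.7(c) is a useful check, but the SAP does not plan to analyse it. A correct guess could also reflect visible improvement rather than disclosure, so the guess alone cannot show which occurred.

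**Conclusion.** The point holds as a gap between a stated requirement and the procedure meant to deliver it. Section 5.1.1 promises a rater without session information, while the subject instruction and 5.2.7 guard only against stated beliefs and formal unblinding. It does not follow that the rater is unprotected, or that ratings will be biased.

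The size is unknown. The range of 2.5 to 10 points (0.125 to 0.5 SD) rests wholly on assumed values of q, s and the SD. It also assumes that every disclosure is decoded correctly and every score moves the expected way. What the documents do fix is the leverage: each rating carries one fifth or one third of its arm mean. This is a cheap improvement to the trial's effect-size estimate, not a flaw that invalidates the design.

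**What to change.** 1. Reword the instruction in 5.1.1, for example: *Before every meeting with the rater, subjects will be asked to say nothing about which dose they or anyone else thinks they received, and nothing about the experimental sessions: experiences, drug effects, reactions or therapists' comments.* What subjects tell the therapists stays unrestricted.
2. Add a step to 5.2.7 repeating this at the start of Visit 12.
3. Add one CRF line, completed before the guess in 5.2.7(c), recording whether session content was disclosed.
4. In the SAP, list flagged subjects beside their CAPS change, and add the rater's Visit 12 guess by arm to the belief table in 9.9.3.1. Both are descriptive.
5. Do not repeat the primary comparison without flagged subjects. Disclosure happens after randomisation and may be related to dose and response, and with 3 against 5 the exclusion could nearly empty an arm.

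The cost is one reworded sentence, a short script, one CRF line and two small outputs. Sample size, alpha, dosing and visits are unchanged. The downside is that subjects must separate how their symptoms are from what happened in the sessions.

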5.1.2 Safety Measures

Safety measures, vital signs and a measurement of psychological distress will be assessed during all experimental sessions. Subjects will rate their current degree of subjective distress with a single-item, self-report scale, the SUD scale, repeatedly during the experimental sessions, with the degree of distress marked along seven points.

The C-SSRS (Hebrew translation) is a clinician-administered measure of suicidal behavior devised to detect potential suicidal thoughts or behaviors during a clinical trial [92]. It consists of a "Baseline" form that assesses lifetime suicidal ideation, ideation intensity and behavior, and a form for assessing current suicidal ideation and behavior. The C-SSRS consists of a series of questions, and can be administered during a face-to-face interview or over the telephone. Suicidality will be assessed at baseline, once during any face-to-face visit, during the second and seventh days of telephone contact, and twice during each experimental session. Subjects who are discontinuing medication to participate in the study will complete the C-SSRS before and after medication washout. The C-SSRS data will be collected on Case Report Forms (CRFs) for all administrations except for the second integrative session, unless an increase in suicidality is observed by the therapists. C-SSRS data from the second integrative session after each experimental session will be kept with the subject's source record.

The therapists will assess general wellbeing during each preparatory session, on each integrative session and integrative telephone calls for seven days.

Blood pressure and heart rate will be assessed periodically during each experimental session. Blood pressure and pulse will be measured at the outset of the experimental session, and once approximately every 30 minutes during the experimental session. More frequent measures will be taken if the established thresholds of 160 systolic, 110 diastolic or pulse of 110 are exceeded. Blood pressure will also be measured more frequently if there are symptoms, such as chest pain, shortness of breath or neurological symptoms,

that may be indicative of hypertension. The therapists will measure subject body temperature approximately every 60 to 90 minutes. Cardiovascular effects will be assessed via blood pressure measurement. The timing of these measurements will be adjusted so they do not interfere with the therapeutic process.

All AEs and spontaneously reported reactions will be collected as described in section 8.5. Adverse events and spontaneously reported reactions may be collected during face to face visits or over the telephone. Commonly reported reactions that are spontaneously reported are collected for seven days after each experimental session on a separate CRF page and will be categorized as mild, moderate or severe.

